Corticosteroids	≥ 14 days after systemic corticosteroids (≥ 5 days) to modify immune AEs. Note: Participants on chronic replacement or a stable/decreasing dose for at least 7 days may be eligible (consult Lilly CRP/CRS)
Live vaccines	≥ 28 days after last live vaccine (seasonal flu vaccines that do not contain a live virus are permitted)

Abbreviations: AE = adverse event; CRP/CRS = clinical research physician/clinical research scientist; NK = natural killer; TBI = total body irradiation.

- [5] The participant has adequate hematologic and organ function ≤ 14 days prior to Day 1 of Cycle 1:

System	Laboratory Value
Hematologic	
Absolute neutrophil count	$\geq 1000/\mu\text{L}$ G-CSF ≤ 7 days prior to C1D1 not allowed Pegfilgrastim ≤ 14 days prior to C1D1 not allowed
Platelets	$\geq 75,000/\text{mm}^3$ Platelet transfusion ≤ 5 days prior to C1D1 not allowed
Hemoglobin	$\geq 8 \text{ g/dL}$ ($\geq 80 \text{ g/L}$) PRBC transfusions ≤ 5 days prior to C1D1 not allowed
Hepatic	
Total bilirubin	$\leq 1.5 \times \text{ULN}$ Exception: $< 3.0 \times \text{ULN}$ for participants with Gilbert Syndrome
ALT and AST	$\leq 3 \times \text{ULN}$ Exception: $\leq 5.0 \times \text{ULN}$ if the liver has tumor involvement

Abbreviations: ALT = alanine aminotransferase; AST = aspartate aminotransferase; C1D1 = Cycle 1 Day 1; G-CSF = granulocyte-colony stimulating factor; PRBC = packed red blood cell; ULN = upper limit of normal.

- Creatinine clearance or calculated GFR $\geq 60 \text{ mL/min/m}^2$ or serum creatinine based on age/gender (see Appendix 5 of the CAMPFIRE Master Protocol) as follows:

Age	Maximum serum creatinine (mg/dL)	
	Male	Female
1 to <2 years	0.6	0.6
2 to <6 years	0.8	0.8
6 to <10 years	1.0	1.0
10 to <13 years	1.2	1.2
13 to <16 years	1.5	1.4
≥ 16 years	1.7	1.5

- [6] Female participants of childbearing potential must have a negative urine or serum pregnancy test within 7 days prior to Cycle 1 Day 1. For France, serum pregnancy test must be performed.

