3.7.4.2. Irinotecan

Irinotecan will be administered at a starting dose of 50 mg/m²/day as an IV infusion over 90 minutes (unless approved otherwise by the Lilly CRP/CRS) on Days 1-5 of each cycle unless interrupted for toxicity. It is recommended to allow a minimum of 20 hours between sequential days of irinotecan dosing.

Participants with prior abdominal/pelvic radiotherapy, or total body irradiation for bone marrow transplantation should have irinotecan dose reduced to 37.5 mg/m²/day at start of therapy.

Impaired glucuronidation: Participants known to have reduced UGT1A1 activity, such as an UGT1A1*28 or UGT1A1*6 allele, may have increased risk of hematological toxicity and/or

diarrhea. An irinotecan dose reduction at the start of therapy should be considered for these participants. Additionally, participants with reduced UGT1A1 activity should be carefully monitored for hematologic toxicities and diarrhea. UGT1A1 testing is not required.

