3.7.8.3.2. Dose Modification for Non-Hematologic Toxicities

Dose Modification for Hepatic Toxicity							
Note: For hepatic toxicities, dose holds, and reductions - apply simultaneously to all drugs as indicated							
Toxicity	Severity	Abemaciclib		Irinotecan		Temozolomide	
		Dose Hold	Dose Reduction	Dose Hold	Dose Reduction	Dose Hold	Dose Reduction
ALT/AST Increased with normal bilirubin	Persistent or recurrent ^a Grade 2	Hold until ≤Grade 1	Reduce 1 dose level	No change		No change	
	Grade 3 ^b			Hold until ≤Grade 1	Reduce 1 dose level	Hold until ≤Grade 1	Reduce 1 dose level
	Grade 4	Discontinue		Discontinue		Discontinue	
ALT/AST Increased with increased bilirubin in the absence of cholestasis	ALT/AST Grade ≥2 and total bilirubin >2× ULN	Discontinue		Discontinue		Discontinue	
Elevated Bilirubin with normal AST/ALT	1.5-2× ULN	No change		Hold until ≤Grade 1	Reduce 1 dose level	No change	
	>2× ULN			Discontinue			

Abbreviations: ALT = alanine aminotransferase; AST = aspartate aminotransferase; ULN = upper limit of normal.

^a Determination of persistent events will be at the discretion of the investigator. Recurrent toxicity refers to the same event occurring within the next 8 weeks (as measured from the stop date of the preceding event).

^b Grade 3 AST/ALT increase (>5× ULN or 5× baseline) is a trigger for additional assessments and hepatic monitoring. See Section 3.9.3.1.1 for additional guidance for hepatic monitoring.

Dose Modification for Diarrhea				
Note: Abemaciclib-associated diarrhea is common in the initial cycles and is less frequent in later cycles. Per investigator’s discretion, dose reductions may be implemented sequentially				
	Abemaciclib		Irinotecan	
Severity and Duration	Dose Hold	Dose Reduction	Dose Hold	Dose Reduction
Grade 2 that does not resolve within 24 hours to ≤Grade 1	Hold until ≤Grade 1	May reduce 1 level	Hold until ≤Grade 1	May reduce 1 level
Grade 2 that persists or recurs ^a after resuming the same dose despite maximal supportive measures	Hold until ≤Grade 1	Reduce 1 dose level		Reduce 1 dose level
Grade 3				
Grade 4			Hold until ≤Grade 1	Reduce 2 dose levels
Any grade that requires hospitalization			Hold until ≤Grade 1	Reduce 2 dose levels

^a Determination of persistent events will be at the discretion of the investigator. Recurrent toxicity refers to the same event occurring within the next 8 weeks (as measured from the stop date of the preceding event).

Dose Modification for ILD/Pneumonitis				

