Note: For ILD/pneumonitis, dose holds, and reductions - apply simultaneously to all drugs as indicated				
Severity	Abemaciclib		Irinotecan	
	Dose Hold	Dose Reduction	Dose Hold	Dose Reduction
Grade 2 that persists or recurs despite maximal supportive measures and does not return to baseline or Grade 1 within 7 days	Hold until \leq Grade 1	Reduce 1 dose level	Hold until \leq Grade 1	Reduce 1 dose level
Grade 3	Discontinue			
Grade 4				

Abbreviation: ILD = interstitial lung disease.

Dose Modification for Venous Thromboembolic Events				
Note: For VTE, dose holds, and reductions - apply simultaneously to all drugs as indicated				
Severity	Abemaciclib		Irinotecan	
	Dose Hold	Dose Reduction	Dose Hold	Dose Reduction
Grade 1 or 2	Hold dose and treat as clinically indicated. Abemaciclib may be resumed when the participant is clinically stable.	No change	Hold dose and treat as clinically indicated. Irinotecan may be resumed when the participant is clinically stable.	No change
Grade 2 Persistent or recurrent ^{a,b}	Hold until resolved	Reduce 1 dose level	Hold until resolved	Reduce 1 dose level
Grade 3				
Grade 4				

^a Determination of persistent events will be at the discretion of the investigator. Recurrent toxicity refers to the same event occurring within the next 8 weeks (as measured from the stop date of the preceding event).

^b that does not resolve with maximal supportive measures within 7 days.

Dose Modification for Non-Hematologic Toxicities						
(Except nausea, diarrhea, ALT/AST increased, VTE, ILD/pneumonitis, or deemed clinically insignificant by the investigator)						
Note: If one drug is considered, by the investigator's judgment, as the most attributable, then initial dose hold and reductions may be made for individual, 2, or all 3 drugs as deemed appropriate by the investigator.						
Severity	Abemaciclib		Irinotecan		Temozolomide	
	Dose Hold	Dose Reduction	Dose Hold	Dose Reduction	Dose Hold	Dose Reduction
Grade 2 Persistent or recurrent ^{a,b}	Hold until ≤Grade 1	Reduce 1 dose level	No change		Hold until ≤Grade 1	No change
Grade 3			Hold until ≤Grade 1	Reduce 1 dose level	Hold until ≤Grade 1	Reduce 1 dose level
Grade 4					Discontinue	

Abbreviations: ALT = alanine aminotransferase; AST = aspartate aminotransferase; ILD = interstitial lung disease.

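### The Gilbert exception admits bilirubin below 3.0× ULN, but with normal AST/ALT every value it newly admits falls in an irinotecan hold or discontinue row at entry

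*Protocol*

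**What the plan says.** Protocol Section 3.6.1.1, criterion 5, sets the hepatic entry limits. Total bilirubin must be at most 1.5× ULN, relaxed to strictly below 3.0× ULN "for participants with Gilbert Syndrome". ALT and AST must be at most 3× ULN, relaxed to 5× ULN "if the liver has tumor involvement".

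The hepatic table in Protocol Section 3.7.8.3.2 has two sets of rows that use bilirubin:

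- Under "Elevated Bilirubin with normal AST/ALT", a value of 1.5-2× ULN leads to an irinotecan hold until Grade 1 or lower and a one-level reduction, with abemaciclib and temozolomide unchanged. Above 2× ULN, irinotecan is discontinued. In the text as extracted, the abemaciclib and temozolomide cells of that row are blank and seem to continue the no-change entry above.
- Under raised ALT/AST together with raised bilirubin, without cholestasis, the trigger "ALT/AST Grade ≥2 and total bilirubin >2× ULN" discontinues all three drugs.

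The table's only baseline-relative wording concerns transaminases, in footnote b: "Grade 3 AST/ALT increase (>5× ULN or 5× baseline". Nothing similar is given for bilirubin. In the supplied documents, Gilbert syndrome is named only in criterion 5.

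**The concern.** One section deliberately lets in people with a constitutionally raised bilirubin. The other, read literally, tells the site to hold or stop part of their chemotherapy because of the same laboratory value. A site that follows the table withdraws irinotecan from a participant the protocol has just declared eligible. A site that regards this as unintended has to improvise on a hepatic safety rule.

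Irinotecan is half of the backbone in both arms, and Protocol Section 3.3.2.5 describes each backbone drug as having little activity on its own. Literal use of the discontinue row would leave an Arm B participant on temozolomide alone and an Arm A participant on temozolomide plus abemaciclib. What is at stake is whether these participants are handled safely and in the same way at every site.

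**Working it through.** No sample-size, power or alpha figure is involved, and the plan states no figure to reproduce. The check sets the eligibility range against the table's triggers.

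**Inputs.** Eligibility limits come from Section 3.6.1.1, criterion 5: bilirubin ≤1.5× ULN in general and <3.0× ULN with Gilbert syndrome; ALT/AST ≤3× ULN in general and ≤5× ULN with liver involvement. Triggers come from the hepatic table in Section 3.7.8.3.2: bilirubin 1.5-2× and >2× ULN with normal AST/ALT; and ALT/AST Grade ≥2 with bilirubin >2× ULN, without cholestasis.

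**Step 1: the range admitted only by the exception.** It runs from above 1.5× to below 3.0× ULN, a width of 3.0 − 1.5 = 1.5 ULN units.

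**Step 2: overlap when AST/ALT is normal.**

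| Bilirubin at entry | Eligible under the exception | Table action on irinotecan | Share of the range |
|---|---|---|---|
| >1.5× to 2.0× ULN | yes | hold, reduce one level | (2.0 − 1.5)/1.5 = 1/3 |
| >2.0× to <3.0× ULN | yes | discontinue | (3.0 − 2.0)/1.5 = 2/3 |

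The shares sum to 1, so no part of the range is free of an action row. They are shares of the laboratory scale, not of participants. For example, a participant with Gilbert syndrome, bilirubin 2.5× ULN and normal AST/ALT is eligible (2.5 < 3.0) and meets the irinotecan discontinue row (2.5 > 2).

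**Step 3: the row that stops all three drugs.** The documents do not say where Grade 2 ALT/AST begins; footnote b gives only Grade 3. Assume that Grade 2 begins above 3× ULN. A participant without liver involvement is capped at 3× ULN and cannot meet this row at entry. One who has Gilbert syndrome, liver involvement, ALT/AST above 3× and up to 5× ULN, bilirubin above 2× and below 3× ULN, and no cholestasis is eligible and does meet it. If Grade 2 began lower, the case would be less narrow.

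**Step 4: where the overlap does not apply.** The isolated-bilirubin rows require normal AST/ALT. A participant whose ALT/AST is abnormal but below Grade 2, with raised bilirubin, falls in no bilirubin row of the table.

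**Step 5: search for an exception elsewhere.**

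- The wording "or deemed clinically insignificant by the investigator" stands in the heading of the separate general non-hematologic table, not the hepatic one, and mentions neither Gilbert syndrome nor bilirubin.
- Section 3.7.4.2 ("Participants known to have reduced UGT1A1 activity") asks sites to consider a lower irinotecan starting dose and to monitor carefully. It sets no bilirubin exception.
- Section 3.9.3.1.1 sets hepatic monitoring triggers by baseline ALT/AST, but keeps total bilirubin at ≥2× ULN in both tiers.

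None of these removes the overlap in Step 2.

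**The case against.** The strongest reply is that the two sections do different jobs. Criterion 5 decides entry; the table governs toxicity. A stable value present before the first dose is arguably not a toxicity. The protocol's adverse-event text supports that view: Attachment 10 excludes expected fluctuation in conditions already present at study start that do not worsen, and treatment emergence is defined by worsening from baseline. On that reading a stable 2.5× ULN on Day 1 triggers nothing. The reading is reasonable, but the table does not state it. Its bilirubin rows are written as laboratory values with no change-from-baseline condition, whereas footnote b shows that the authors wrote a baseline multiple for transaminases.

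The second reply is that governing text may exist out of sight. The criteria to begin each cycle (Section 3.5.1.1) are redacted, the opening of Section 3.7.8.3 is not in the extract, and the Master Protocol was not supplied. The grading standard behind the hold row's release condition is cited but not reproduced. All of this stands: the absence of an exception is established only for the text available. It remains true that the hepatic table points to no such rule.

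A reader might also infer more than the documents support:

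- That bilirubin alone stops all study treatment. The isolated rows act on irinotecan only; abemaciclib and temozolomide appear unchanged.
- That every eligible participant with Gilbert syndrome above 1.5× ULN is caught. The isolated rows apply only with normal AST/ALT.
- That the treatment comparison is biased. Both arms receive the same irinotecan regimen under the same rows, and nothing in the documents shows that the conflict would arise or be handled differently by arm.

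**Conclusion.** Wrong as written: an internal contradiction between criterion 5 and the hepatic table, limited to bilirubin above 1.5× and below 3.0× ULN. With normal AST/ALT the overlap covers that whole range, and its effect is confined to irinotecan. The overlap with the all-drug row is real but narrow, and its extent depends on the assumed Grade 2 threshold.

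The documents give no count of participants with Gilbert syndrome, so the number affected is unknown and may be zero. One participant would be 1/45 = 2.2% of the minimum enrolment; that is a unit of scale, not an estimate of effect. The conclusion rests on the visible text, and a rule in the redacted or unsupplied parts could resolve it. It is worth correcting because a stated rule, followed literally, stops backbone chemotherapy in a participant whom the protocol expressly admits.

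**What to change.** Reconcile criterion 5 in Section 3.6.1.1 with the bilirubin rows in Section 3.7.8.3.2. Add a footnote to the hepatic table stating whether and how those rows, including the combined ALT/AST and bilirubin row, apply to participants enrolled under the Gilbert exception. If a governing rule already exists in the cycle-start criteria, the opening of Section 3.7.8.3 or the Master Protocol, a cross-reference from the table is enough. The clinical content is for the sponsor to decide, and none is proposed here.

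The cost is one clarification at the next amendment. It changes no endpoint, sample size or analysis.

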3.6.2. Exclusion Criteria

Participants will be excluded from Study JP04 if they meet any of the exclusion criteria in Section 6.2 of the CAMPFIRE Master Protocol or the following criteria:

- [42] Have received any prior CDK4 and 6 inhibitor
- [43] Progression during prior treatment with irinotecan and/or temozolomide
- [44] Have a known intolerance or hypersensitivity, such as urticaria, allergic reaction including anaphylaxis, toxic necrolysis, and Stevens-Johnson syndrome, to any of the study treatments or dacarbazine
- [45] Diagnosed and/or treated additional malignancy within 3 years prior to enrollment that, in the judgment of the investigator and Lilly, may affect the interpretation of results, with the exception of curatively treated basal cell carcinoma of the skin, squamous cell carcinoma of the skin, and/or curatively resected in situ cervical and/or breast cancers
- [46] A serious and/or uncontrolled preexisting medical condition(s) that, in the judgment of the investigator, would preclude participation in this study (such as severe myelosuppression, interstitial lung disease, severe dyspnea at rest or requiring oxygen therapy, current bowel obstruction, history of major surgical resection involving the stomach or small bowel, or preexisting Crohn's disease or ulcerative colitis or a preexisting chronic condition resulting in clinically significant diarrhea).

3.6.2.1. Exceptions to the CAMPFIRE Master Protocol Exclusion Criteria

There are no exceptions to the CAMPFIRE Master Protocol exclusion criteria.

3.6.3. Lifestyle Restrictions

Participants should refrain from consuming grapefruit, grapefruit juice, and grapefruit-containing products while on study due to the effect on CYP3A4.

3.6.4. Screen Failures

This section should be used in place of Section 6.4 of the CAMPFIRE Master Protocol.

Screen failures are defined as participants who consent/assent to participate in the clinical study but are not subsequently entered in the study. A minimal set of screen failure information is required to ensure transparent reporting of screen failure participants to meet the Consolidated Standards of Reporting Trials publishing requirements and to respond to queries from regulatory authorities. Minimal information includes demography, screen failure details, eligibility criteria, and any SAE.

Individuals who do not meet the criteria for participation in this study (screen failure) may be rescreened. Individuals may be rescreened 1 time. The interval between rescreening should be ≥ 2 weeks. Each time rescreening is performed, the individual and/or the individual's legally acceptable representative, parent(s), or legal guardian (when applicable) must sign a new informed consent form (ICF) and assent (if applicable) and will be assigned a new identification number. Repeating of laboratory tests during the screening period or repeating screening tests to comply with the protocol-designated screening period does not constitute rescreening.

Screening must occur within 28 days of Cycle 1 Day 1, but a 7-day window beyond 28 days is acceptable without being considered as a protocol deviation or screen fail.

3.7. Treatments

3.7.1. Treatments Administered

Table JP04.6 shows the treatment regimens.

Table JP04.6. Treatment Regimens

Starting Doses Cycle = 21 days				
	Abemaciclib PO		Irinotecan IV (Days 1-5 each cycle)	Temozolomide PO (Days 1-5 each cycle)
	<18 years	≥18 years		
Arm A	55 mg/m ² BID (max dose 100 mg BID)	100 mg BID	50 mg/m ² /day × 5	100 mg/m ² /day × 5
Arm B	None		50 mg/m ² /day × 5	100 mg/m ² /day × 5
Authorized as defined by EU Clinical Trial Regulation	Authorized and not used according to EU authorization		Authorized and not used according to EU authorization	Authorized and not used according to EU authorization

Abbreviations: BID = twice daily; IV = intravenous; PO = orally.

Participants will begin dosing-assigned treatment on Cycle 1 Day 1. A cycle is defined as an interval of 21 days timed to irinotecan and temozolomide. The 21-day cycle, anchored to irinotecan and temozolomide, should be maintained throughout the treatment phase. Cycles may not be less than 21 days.

When delays are required, doses should be resumed at the earliest medically appropriate opportunity based on investigator judgment and dose adjustment guidelines (Section 3.7.8).

Treatment will continue until progression, unacceptable toxicity, or other discontinuation criteria are met (Section 3.8).

A delay to the start of a cycle of a dose due to holiday, weekend, weather, or other unforeseen circumstances will be permitted for a maximum of 7 days and not counted as a protocol deviation. In exceptional circumstances, a delay of >7 days is permitted upon agreement between the investigator and the Lilly CRP/CRS. Abemaciclib treatment may continue during the delay if there is sufficient drug supply and if there are no toxicities that would prevent treatment.

Irinotecan and temozolomide must be administered on 5 consecutive days.

Packaging and labeling

Treatments administered in the study will be supplied by the sponsor in accordance with current Good Manufacturing Practice. Study interventions will be labeled as appropriate for country requirements.

3.7.2. Method of Treatment Assignment

Before each participant's enrollment into the study, an eligibility check must be conducted by the investigational site. Upon confirmation of eligibility, the site will register the participant by assigning the participant a unique study identification number via the IWRS, which is accessible 24 hours a day. Study treatment will be allocated to participants using the IWRS. Participants who meet all enrollment criteria will be randomly assigned to receive study treatment.

Participants will be stratified by

- time to first recurrence (< 2 or ≥ 2 years from initial diagnosis) (Leavey et al. 2008),
- isolated pulmonary metastases vs other metastases (Leavey et al. 2008), and
- age (< 18 years or ≥ 18 years).

3.7.3. Blinding

This is an open-label study. The participant, caregiver, and all staff involved in treating and caring for study participants will have full knowledge of treatment assignments.

To maintain the scientific integrity of this trial, the study team's access to aggregate safety and efficacy data will be strictly controlled prior to the interim and final analyses. Access to the electronic data capture (eDC) system will be limited to those who require this information for their role, and all access will be documented.

For the accumulated aggregate database, that is, the database to which Lilly statisticians (or those of its designee) have access, treatment assignment and other parameters that can disclose treatment assignment will be scrambled or masked. Therefore, the sponsor and all investigative sites will remain blinded to treatment group assignments for the aggregate database until the database lock for the final analysis. Scrambled treatment assignments will be used in the reporting database until the study reaches its final analysis or the study is determined to be positive by the DMC. During this time, analyses using unblinded treatment codes will be performed only at the interim analysis points specified in the protocol/SAP.

For those safety and efficacy analyses assigned to the DMC, only the designated SAC, which is independent of the sponsor, will perform analyses on unblinded data, that is, an aggregate database with correct treatment assignments.

Further details are included in the study blinding plan.

3.7.4. General Dosing Instructions

Obesity: For participants with a BMI ≥ 30 kg/m², the American Society of Clinical Oncology Guidelines recommends calculation of dose using the actual body weight for calculation of body surface area- or weight-based dosing (ASCO [Griggs et al. 2012]).

For each cycle, the actual dose administered for study drugs must be within 10% of the planned dose; any total cycle dose that is not within 10% (either $> 110\%$ or $< 90\%$) of the planned dose will result in a protocol deviation. Please contact the Lilly CRP/CRS to discuss any questions for individual situations.

